6.6.1.4 Management of hypertension

Early identification and treatment of hypertension is recommended. Evaluate for other or concomitant causes. Assess renal function as well as urinalysis. For recurrent or persistent hypertension (systolic blood pressure >140 mmHg or diastolic blood pressure >90 mmHg) treat according to institutional guidelines with the goal of therapy to reduce blood pressure to <140 mmHg systolic/90 mmHg diastolic. Hypertension associated with life-threatening consequences (eg, malignant hypertension, neurological deficits, hypertensive crisis), permanently discontinue treatment (either SAR442720 and pembrolizumab or SAR442720 and adagrasib).

Please refer to [Table 27](#) for dose modifications guidelines. Cardiology or nephrology consultation should be considered, as clinically indicated.

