6.6.1.3 Management of ophthalmologic complications

The causal relationship between a change in vision and the study treatment should be carefully explored and an ophthalmologist should be consulted. Immediate consultation should be sought for Grade >1 visual changes. Special attention should be given to retinal (eg, central serous retinopathy [CSR]) or retinal vein abnormalities (eg, RVO). If consultation cannot be obtained within 7 days of onset, interrupt treatment (either SAR442720 and pembrolizumab or SAR442720 and adagrasib) until the consultation has occurred.

If RVO is diagnosed, permanently discontinue treatment (either SAR442720 and pembrolizumab or SAR442720 and adagrasib) immediately and treat per institutional guidelines. If uveitis is diagnosed, withhold treatment (either SAR442720 and pembrolizumab or SAR442720 and adagrasib) and consider use of topical steroids until resolution. If CSR or neurosensory retinal detachment is diagnosed, withhold treatment until symptoms resolve and retinal exam shows resolution. Restart medication(s) at one dose level lower and close monitoring following re-initiation of medication(s). If > Grade 1 symptoms recur or follow-up ophthalmology examination worsens, withhold treatment (either SAR442720 and pembrolizumab or SAR442720 and adagrasib) and either further decrease the dose or permanently discontinue treatment.

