10.3.3 Recording and follow-up of AE and/or SAE

AE and SAE recording

- When an AE/SAE occurs, it is the responsibility of the Investigator to review all documentation (eg, hospital progress notes, laboratory reports, and diagnostics reports) related to the event.
- The Investigator will then record all relevant AE/SAE information in the CRF.
- It is **not** acceptable for the Investigator to send photocopies of the participant's medical records to the Sponsor in lieu of completion of the AE/SAE CRF page.

- There may be instances when copies of medical records for certain cases are requested by the Sponsor. In this case, all participant identifiers, with the exception of the participant number, will be redacted on the copies of the medical records before submission to the Sponsor.
- The Investigator will attempt to establish a diagnosis of the event based on signs, symptoms, and/or other clinical information. Whenever possible, the diagnosis (not the individual signs/symptoms) will be documented as the AE/SAE.

Assessment of intensity

Adverse events will be graded according to the NCI CTCAE Version 5.0. NOTE: The seriousness and intensity of an event are assessed independently of each other. An event is defined as “serious” when it meets at least 1 of the predefined criteria as described in the above definition of an SAE, and can be assessed as any grade. A nonserious event may be assessed as either CTCAE Grade 1 or 2. Although CTCAE Grade 3 nonserious events are possible in some circumstances, the Investigator should carefully consider whether the event is best classified as serious. Any AE which is either a CTC Grade 4 (life threatening) or Grade 5 (has death as an outcome) is by definition an SAE.

Assessment of causality

- The Investigator is obligated to assess the relationship between study intervention and each occurrence of each AE/SAE.
- A “reasonable possibility” of a relationship conveys that there are facts, evidence, and/or arguments to suggest a causal relationship, rather than a relationship cannot be ruled out.
- The Investigator will use clinical judgment to determine the relationship.
- Alternative causes, such as underlying disease(s), concomitant therapy, and other risk factors, as well as the temporal relationship of the event to study intervention administration will be considered and investigated.
- The Investigator will also consult the IB and/or Product Information, for marketed products, in his/her assessment.

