10.9 APPENDIX 9: GENERAL GUIDELINES FOR THE MANAGEMENT OF ADVERSE EVENTS

Investigators must be extremely vigilant and be ready to intervene early in the management of AEs, particularly immune-related AEs because the onset of symptoms of irAEs (eg, pneumonitis) may be subtle.

- Detailed guidance for the management of specific AEs (colitis, endocrine AE, pneumonitis, renal AE, dermatologic AE, hepatitis, ophthalmologic AE [uveitis], etc.) is provided in [Table 27](#).
- General guidance is provided in [Table 26](#) below.
- If a participant experiences several AEs which involve different recommendations, the most conservative recommendation should be followed.

The recommendations provided in [Table 26](#) and [Table 27](#) should be seen as guidelines, and the treating physician should exercise clinical judgment based on the symptoms and condition of the individual participant.

Table 26 - General guidelines

Severity	Withhold/restart /discontinue SAR442720 treatment	Withhold/restart/discontinue the combination drug (Pembrolizumab or adagrasib) treatment	Supportive care
Grade 1	No action	No action	Provide symptomatic treatment.
Grade 2	No action	May delay or omit the pembrolizumab dose until Grade ≤ 1 Adagrasib dose modification/ dose interruption per Investigators discretion unless otherwise defined in Table 27 .	Consider systemic corticosteroids (Prednisone 0.5 to 1 mg/kg/day or equivalent) in addition to appropriate symptomatic treatment.
Grade 3	Delay the treatment until toxicity improves to Grade ≤ 1 or baseline.		For any Grade 3-4 immune-related adverse event, if symptoms worsen or do not improve on adequate corticosteroids (prednisone 1 to 2 mg/kg/day or equivalent) within 48 to 72 hours), consider additional immunosuppressive agents (to be selected from agents such as: infliximab, cyclophosphamide, cyclosporine and mycophenolate mofetil). Referral of the participant to a specialized unit for assessment and treatment should be considered.
Grade 4	Permanently discontinue		

Table 27 - Dose modification guidelines for combination regimens (SAR442720 and pembrolizumab combination or SAR442720 and adagrasib combination)

AE	Action

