Skin reactions	
Grade 1 or 2 (tolerable): Administer supportive care and continue study drugs
 
Intolerable Grade 2-Grade 3: Hold both drugs until < Grade 2. If improves to < Grade 2 within 4 weeks, then reduce SAR442720 by one dose level and resume combination drugs at the same dose level.
 
Suspected Stevens-Johnson Syndrome (SJS) or toxic epidermal necrolysis (TEN): Withhold both drugs until adverse reactions recover to Grade 0-1.
 
Grade 4: Hold both drugs until < Grade 1. If improves to < Grade 1 within 4 weeks, resume, reduce SAR442720 by two dose levels and resume combination drugs at the same dose level.
 
Grade 4 or confirmed SJS or TEN: Permanently discontinue both drugs
 
If \geq Grade 3 rash recurs despite two SAR442720 dose level reductions, permanently discontinue both drugs.
 
If rash does not improve within 4 weeks, permanently discontinue both drugs.

Ocular symptoms > Grade 2	
Hold both study drugs and obtain ophthalmology consult.
 
RVO: Any grade, permanently discontinue both drugs (Part-1, 2, and 4 only). In Part-3 permanently discontinue SAR442720 but may continue adagrasib, please consult with the Medical Monitor.
 
Neurosensory retinal detachment: Hold both drugs until resolution to \leq Grade 1. If resolves within 4 weeks, then reduce SAR442720 by one dose level. If visual symptoms > Grade 2 recur despite two dose level reductions, permanently discontinue both drugs. (Part-1, 2 and 4 only). In Part-3 permanently discontinue SAR442720 but may continue adagrasib, please consult with the Medical Monitor.
 
Uveitis/iritis > Grade 2: Hold both study drugs. If resolves to \leq Grade 1 within 4 weeks, then reduce SAR442720 dose by one level and resume both study drugs. If recurs despite two dose level reductions of SAR442720, permanently discontinue both drugs. If > Grade 1 symptoms recur or follow-up ophthalmology examination results worsen, withhold treatment (either SAR442720 and pembrolizumab or SAR442720 and adagrasib) and either further decrease dose or permanently discontinue treatment.
 
Other > Grade 2 AE: Hold SAR442720. If AE doesn't improve within 2 weeks, then consider holding the combination drug. If no improvement within 4 weeks from onset, consider permanently discontinuing both drugs. In ambiguous cases, please consult with the Medical Monitor.

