Reduction in LVEF and other cardiac toxicities	
Asymptomatic reduction: absolute decrease in LVEF \geq 20% from baseline and below LLN, withhold treatment (either SAR442720 and pembrolizumab or SAR442720 and adagrasib) for up to 4 weeks and repeat echocardiogram (ECHO) for LVEF at 2, 4, 10, and 16 weeks after hold. Restart at reduced dose if LVEF \geq LLN and absolute decrease from baseline LVEF $<$ 20%. Permanently discontinue if symptoms of heart failure are present.
 
Symptomatic reduction: In case of symptomatic systolic dysfunction with an LVEF decrease from baseline \geq 10% and/or below LLN, withhold both SAR442720 and pembrolizumab for up to 4 weeks and consider permanent discontinuation if considered causative; in Part-3 permanently discontinue SAR442720 and adagrasib. Consult cardiology and the Medical Monitor.
 
If reinitiating treatment, ALL of the following must be present: an EF decrease not considered to be associated with the study drug, symptoms resolve, LVEF $>$ LLN, and absolute decline from baseline was $<$ 10%; otherwise, permanently discontinue both drugs.
 
If reinitiating treatment, restart both study drugs, SAR442720 and adagrasib at a lower dose (pembrolizumab dose reduction is not allowed). Please consult with the Medical Monitor for individual cases.
 
All participants who require dose reduction of SAR442720 due to treatment related systolic dysfunction should have ECHO at 2 weeks, 4 weeks, 10 and 16 weeks, then per protocol or as clinically indicated.
 
In Part-3:
 
For all other Grade \geq 3 cardiac toxicities/adverse drug reactions hold study treatment until recovery to \leq Grade 1 or to baseline. Adagrasib/SAR442720 treatment may resume at one dose level lower. For QTc prolongation please refer to the previous bullet. Please consult with the Medical Monitor for individual cases.

Hypertension	
Grade 2: Treat according to institutional guidelines with goals blood pressure $<$ Grade 1. Continue both drugs.
 
Grade 3: Treat according to institutional guidelines with goal blood pressure $<$ Grade 1. Consider holding SAR442720 and continue pembrolizumab and adagrasib. If improved restart SAR442720 at reduced dose level.
 
Grade 4: Treat according to institutional guidelines. Discontinue both SAR442720 and pembrolizumab. In Part-3 hold adagrasib until \leq Grade 1 or baseline, then may resume one dose level lower.

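### In Part-3, Sections 6.6.1.4 and 6.6.1.3 permanently stop adagrasib after life-threatening hypertension and after retinal vein occlusion, while Table 27 lets it resume or continue, and no text says which governs.

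*Protocol*

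**What the plan says.** **Hypertension.** Protocol Section 6.6.1.4, on hypertension with life-threatening consequences: "hypertensive crisis), permanently discontinue treatment (either SAR442720 and pembrolizumab or SAR442720 and adagrasib". The section then refers to Table 27 "for dose modifications guidelines. Cardiology or nephrology consultation should be considered, as clinically indicated". The Grade 4 hypertension entry of Table 27 (Appendix 9, Section 10.9) says: "Discontinue both SAR442720 and pembrolizumab. In Part-3 hold adagrasib until" the event has come down to at most "Grade 1 or baseline, then may resume one dose level lower".

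**Retinal vein occlusion.** Section 6.6.1.3: "If RVO is diagnosed, permanently discontinue treatment (either SAR442720 and pembrolizumab or SAR442720 and adagrasib) immediately". The ocular row of Table 27: "RVO: Any grade, permanently discontinue both drugs (Part-1, 2, and 4 only). In Part-3 permanently discontinue SAR442720 but may continue adagrasib", with a request to consult the Medical Monitor.

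**Status of the tables.** Appendix 9 says that the recommendations in Tables 26 and 27 "should be seen as guidelines, and the treating physician should exercise clinical judgment". It also has a rule that the most conservative recommendation is followed, but that rule is written for a participant who has several adverse events with differing recommendations.

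**The concern.** These are current safety instructions on the same drug after the same events, and they lead to different actions. An investigator who follows Section 6.6.1 never gives adagrasib again. One who follows Table 27 may restart it after a life-threatening hypertensive event, or never interrupt it for RVO. Both events are serious by the protocol's own standard: Section 4.1.1 makes treatment-related Grade 4 events and RVO of any grade dose-limiting when they occur in Cycle 1.

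There is a smaller reporting effect. SAP Table 5 counts events leading to permanent discontinuation of adagrasib and to permanent full discontinuation, and both counts can depend on which text a site followed. A site that resumes adagrasib under Table 27 also departs from Section 6.6.1.4. Section 8 treats adherence to the design as required, and SAP Section 4.2 summarises critical and major deviations.

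**Working it through.** The point is textual, so the check sets the instructions side by side and then looks for anything that ranks them.

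| Event in Part-3 | Section 6.6.1 | Table 27 | SAR442720 | Adagrasib |
|---|---|---|---|---|
| Life-threatening / Grade 4 hypertension | 6.6.1.4: stop both permanently | Stop SAR442720; hold adagrasib to Grade 1 or lower or baseline, then may resume one level lower | Same | **Conflict** |
| RVO, any grade | 6.6.1.3: stop both permanently and at once | Stop SAR442720; adagrasib may continue, consult Medical Monitor | Same | **Conflict** |

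**Do the two hypertension texts cover the same event?** Section 6.6.1.4 speaks of life-threatening consequences and Table 27 of Grade 4. Section 10.3.3 links them: "Any AE which is either a CTC Grade 4 (life threatening) or Grade 5 (has death as an outcome) is by definition an SAE". They overlap.

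**Could Section 6.6.1 be meant for pembrolizumab only?** No. Both sentences name adagrasib. For the pembrolizumab parts, the two sources agree.

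**Does any text set precedence?**

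1. Section 6.6.1.4 refers to Table 27 straight after ordering a permanent stop, without saying that the table overrides the order. Section 6.6.1.3 has no reference to the table at all.
2. Section 6.6.1.1 sends adagrasib interruptions and modifications to Appendix 9 but does not place it above 6.6.1.3 or 6.6.1.4.
3. Section 6.6 says dose modifications follow the criteria and guidelines in Section 6.6.1. It does not rank that section against the appendix.
4. Appendix 9 calls its tables guidelines subject to judgment. If anything this favours Section 6.6.1, but it is not a ranking.
5. The most-conservative rule concerns several events in one participant, not two instructions for one event.
6. Table 26 gives permanent discontinuation as general Grade 4 guidance. That agrees with 6.6.1.4 and leaves the hypertension entry of Table 27 still in conflict.
7. Section 7.1.1 lets adagrasib continue when SAR442720 must stop, if the Study Medical Manager agrees. This is a general permission. It does not address events for which another section orders adagrasib itself stopped.

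None of the seven settles the matter.

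**Is the permission in Table 27 complete?** Table 14 lists adagrasib at 400 mg BID in four of six levels (DL-1, DL1, DL2, DL3b) and at 600 mg BID in two (DL3a, DL4). Table 17 lists the same two doses.

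- From 600 mg BID, one level lower is 400 mg BID, which is listed. Two levels lower is not listed.
- From 400 mg BID, one level lower is not listed.

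A participant at 400 mg BID who resumes after Grade 4 hypertension would therefore have no defined dose. The QTcF row of Table 27 (one or two levels lower) and Section 6.6.1.1 (a lowest anticipated dose) presuppose lower levels that neither table gives.

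**The case against.** The strongest reply is that the texts can both be obeyed. Section 6.6.1 gives an order and Table 27 only a permission, so a site that stops adagrasib breaches neither. Table 27 is also the wording tailored to Part-3, while the parenthesis in Section 6.6.1 is a stock phrase repeated across several subsections. On this reading the sponsor meant to exempt adagrasib and overlooked the body text. Continuation is gated in any case by the Study Medical Manager and, for RVO, by the Medical Monitor. The study is uncontrolled, no effect on the response rate or maximum tolerated dose is shown, and discontinuation counts simply record what was done.

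Part of this stands. The exemption may well be intended, which is why the fix leaves that route open. The gates limit the harm, and the reach is narrow. But a permission to give a drug that another section orders permanently stopped is still a conflict for anyone considering its use. The gates settle who must agree, not which instruction those people should apply. The documents do not show which text reflects the sponsor's intention. The protocol does align the two sources elsewhere: for symptomatic loss of ejection fraction, Section 6.6.1.7 and Table 27 carry the same Part-3 instruction.

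**Conclusion.** The concern holds. Two entries, Grade 4 hypertension and RVO, contradict each other for adagrasib in Part-3, and nothing in the protocol resolves them. This should be fixed.

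The size is limited. SAR442720 stops under either text, so its discontinuation counts do not change. Dose-limiting toxicity status is decided under Section 4.1.1 whatever happens to adagrasib afterwards, and no effect on the response rate or maximum tolerated dose is claimed. The reporting effect is confined to counts of permanent adagrasib discontinuation and of full discontinuation. The documents give no rate for either event with this combination, so no number of affected participants can be stated. The hypertension half rests on reading Grade 4 as life-threatening, as Section 10.3.3 does.

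**What to change.** Make the two sources identical for adagrasib in Part-3.

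- **Default.** Change the Part-3 entries of Table 27 for Grade 4 hypertension and for RVO to permanent discontinuation of both drugs. This is the one course that already complies with both texts. Its cost is clinical: a participant benefiting from adagrasib could not resume or continue it after either event.
- **If the exemption is intended.** Add one sentence each to Sections 6.6.1.3 and 6.6.1.4 exempting adagrasib in Part-3 on the terms of Table 27, and name the adagrasib dose or doses below 400 mg BID so that a lower level exists for every participant.

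Either route is a wording change and needs no new assessments or data.

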6.6.1.5 Management of rhabdomyolysis or symptomatic CPK increase

Assess for other causes of CPK elevation and rhabdomyolysis such as strenuous exercise, trauma, heat-related causes, ischemia, inflammatory process, etc. For CPK elevations, rule out cardiac causes by obtaining ECG, cardiac troponin, and CK-MB fraction. Evaluate for rhabdomyolysis and potential renal compromise with a clinical examination, urinalysis, and complete blood chemistry (eg, metabolic panel). Treat according to institutional guidelines. Early IV hydration with urine alkalization provided that there are no contraindications. Nephrology consultation should be considered, as clinically indicated.

6.6.1.6 *Management of liver function abnormalities and hepatotoxicity*

Assess whether metastatic disease to the liver is contributing to liver function abnormalities and/or hepatotoxicity. Evaluate for infections or other causes of increased liver function abnormalities if appropriate. Consider imaging of the liver. Hold or dose reduce concomitant medications which may potentiate hepatotoxicity or metabolized by the liver. Evaluate extent of liver injury (eg, albumin level, PTT, INR) and if there is evidence of severe injury, then discontinue treatment (either SAR442720 and pembrolizumab or SAR442720 and adagrasib).

Please refer to [Table 27](#) for dose modifications guidelines for LFTs.

6.6.1.7 *Management of decrease in left ventricular ejection fraction*

Asymptomatic absolute decrease in LVEF from baseline $\geq 20\%$ from baseline and below LLN, withhold treatment (either SAR442720 and pembrolizumab or SAR442720 and adagrasib) for up to 4 weeks and repeat echocardiogram (ECHO) for LVEF at 2, 4, 10, and 16 weeks after treatment was withheld. Restart at reduced dose if LVEF \geq LLN and absolute decrease from baseline LVEF $< 20\%$. Permanently discontinue if symptoms if symptoms of heart failure are present.

Symptomatic reduction: In case of symptomatic systolic dysfunction with an LVEF decrease from baseline $\geq 10\%$ and/or below LLN, withhold both SAR442720 and pembrolizumab for up to 4 weeks and consider permanent discontinuation if considered causative; in Part-3 permanently discontinue SAR442720 and adagrasib.

Please refer to [Table 27](#) for dose modifications guidelines. Cardiology consultation should be considered.

6.6.1.8 *Management of hemorrhage*

Evaluate complete blood count and coagulation laboratories. Transfuse blood products and correct coagulation abnormalities as per institutional guidelines. Withhold treatment (either SAR442720 and pembrolizumab or SAR442720 and adagrasib) if hemorrhage associated with thrombocytopenia, reduced platelet count from baseline, or at the discretion of investigator.

Please refer to [Table 27](#) for dose modifications guidelines.

6.6.1.9 *Management of pyrexia*

Evaluate for source of fever. Obtain a complete blood count (CBC). Routine infectious work-up and treatment with antibiotics may not be necessary for participants with uncomplicated pyrexia without localizing symptoms; but work-up may be completed and antibiotic may be given, based on the clinical assessment. Hold pembrolizumab until fever resolves and restart with same dose and schedule. SAR442720 or adagrasib may be held at the investigator's discretion. Antipyretics may be given for treatment or as prophylaxis in participants with recurrent pyrexia associated with a medication. Consider short-course of low-dose corticosteroids for recurrent/recalcitrant fevers. Evaluation blood chemistry (ie, renal function test) for those with severe pyrexia.

6.6.1.10 Management of fatigue

Other causes of fatigue should be evaluated (eg, infection, disease progression and hematological, electrolyte, heart failure and endocrine abnormalities). Dose-modification and/or low-dose corticosteroids may be considered.

6.6.1.11 Pneumonitis

Respiratory symptoms such as cough, shortness of breath, etc. should be investigated with a chest X-ray or chest CT scan. Evaluate for possible infections and other causes of respiratory compromise including progressive pulmonary disease, cardiac dysfunction, etc.

